## II. SPECIFIC AIMS

The specific aims of this experiment are as follows:

[figure not shown]
- **Aim 1: To evaluate the efficacy of tDCS and mirror therapy (MT) as rehabilitative tools for the management of chronic PLP patients.**

We will explore the aim 1 in a randomized factorial controlled trial in which patients will be assigned to one of four groups: active tDCS and active MT; sham tDCS and active MT; active tDCS and sham MT (which consists of using a covered mirror for the therapy); and both sham tDCS and sham MT (covered mirror).

The primary end point will be severity of pain measured by changes in PLP as indexed by a Visual Analog Scale (VAS). The study will require a total of 13 weeks to be completed. The first week, each patient will give daily reports of their pain using a VAS, accounting for their PLP experience in the past 24hs. This initial baseline week will be followed by 4 weeks of treatment (tDCS and/or MT) and a final 8-week follow-up period without any treatment to examine long-lasting effects of each therapy. *Our hypothesis is that the combined intervention (tDCS and MT) will result in a greater pain reduction as compared with any therapy alone and no therapy.*

- **Aim 2: To examine the mechanisms underlying PLP using two neurophysiological techniques.**

For each of the four groups described in aim 1, we will determine the neural correlates of the effect. We will use single-pulse and paired-pulse transcranial magnetic stimulation (TMS) to assess cortical mapping and cortical excitability changes associated with cortical reorganization. We will also use functional magnetic resonance imaging (fMRI) to assess brain changes, including the quantification of maladaptive cortical reorganization. Using fMRI, we will determine the changes in Blood-Oxygen-Level dependent activation between the sensory-motor cortex of the affected and unaffected side after the treatment. We will compare these neurophysiological parameters before and after treatment in each of the four groups. *Our hypothesis is that the combined group (tDCS and mirror therapy) will have a greater activation than any therapy alone and also than the no therapy group (sham tDCS and covered mirror). This effect will also be correlated with pain reduction.*

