**Visit 3**

fMRI Evaluation – (Approximate Time: 1 hour)

*\*\*Visits 1-3 may be completed on the same day or broken up into two or three separate visits as the subject prefers*

**Visit 4 – 12** (Approx Time: 45 minutes)

Intervention visits: tDCS + Mirror Therapy

*This visit will be scheduled within 1 week after the baseline measurements are done.*

In the first 2 weeks subjects will receive tDCS (\*sham or active) and mirror therapy (sham or active). There will be 10 stimulation visits to be completed in these 2 weeks (ideally Monday to Friday, 5 days each week). The subject will receive 20 minutes either of active or sham tDCS per day and 15 min of active or sham mirror therapy sessions. The subjects will receive the intervention according to the prior randomized group.

Before stimulation, the subject will complete the following assessments:

- VAS Phantom Limb Pain
- VAS for Stump pain
- VAS for Phantom Limb Sensation
- VAS for Phantom Limb Telescoping

After each session, subjects will complete the following assessments:

- Side Effects Questionnaire for tDCS
- VAS Phantom Limb Pain
- VAS for Stump pain
- VAS for Phantom Limb Sensation
- VAS for Phantom Limb Telescoping

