**Visit 16:**

First Follow Up Visit – (Approx Time: 1 hour)

*This visit will be scheduled ~ four weeks (+/- 5 days) after the last MT home session and the following assessments will be performed:*

- Visual Analogue Scale (VAS) for phantom limb pain
- Visual Analogue Scale (VAS) for Stump pain.
- Visual Analog Scale (VAS) for Phantom Limb Sensation
- Visual Analog Scale (VAS) for Phantom Limb Telescoping
- Beck Anxiety Inventory
- Beck Depression Inventory
- Pain Medication uses diary

*\*\*Visit 16 may be completed by terms of phone interview as the subject prefers.*

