**Visit 17:**

Last Follow Up Visit - (Approx Time: 2 hours)

*This visit will be schedule ~eight weeks (+/- 5 days) after the last MT home session and the following assessments will be performed:*

[figure not shown]
- Visual Analogue Scale (VAS) for phantom limb pain
- Visual Analogue Scale (VAS) for Stump pain
- Visual Analog Scale (VAS) for Phantom Limb Sensation
- Visual Analog Scale (VAS) for Phantom Limb Telescoping
- Pain Medication uses diary.
- Stroop Test.
- Health Survey SF-36.
- Beck Anxiety Inventory
- Beck Depression Inventory
- Single and paired pulse TMS
- Side Effects Questionnaire for TMS
- Blinding questionnaire

[figure not shown]
*\*\*After visit 14 until the end of the trial participation, the co-investigator will try to contact the subjects 3 times per week to acquire pain diary and medication changes data. We are going to try maximum 2 attempts per day.*

The schedule for the subjects can be seen in table 1, which illustrates the procedures that will be performed at each visit:

**Table 1:** Visits Schedule

	Consent and Screening	Baseline	fMRI Visit	Interventions Session	fMRI Visit	Follow-Up
--	------------------------------	-----------------	-------------------	------------------------------	-------------------	------------------

observed in the mirror to their phantom limb and to keep their attention focused on the task. Instructions will be explained verbally, demonstrated by a therapist, and performed by the subject in front of the therapist during the first two weeks (the MT sessions will be scheduled back-to-back with the tDCS sessions). After this training, subjects will continue MT everyday for 2 more weeks at home. Subjects will be instructed to stop MT if it intensifies their pain, and to document if this happens

- Sham Mirror Therapy (Covered MT): Subjects will be asked to perform movements in the same way that the active group but with a covered mirror.

[figure not shown]

Figure 1: Schematic view of the experiment in time points: baseline, procedures, subjects enrolled intervention, first follow-up and second follow up.

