*Pain and medication diary:* To help monitor pain levels and medication use information, as well as safety. Subjects will be asked to record the number of phantom limb episodes on a daily basis, using a pain diary. They will record the intensity of the strongest episode as well as phantom limb sensation and stump pain on a colored visual analog scale included in the diary, where 0 represents no pain at all and 10 represents the highest pain the patient has ever felt. Moreover subjects will record their current medications and dosages daily in a pain medication diary, until completion of the study.

*Beck Depression Inventory:* This self-report inventory consists of 21 multiple-choice questions and is widely used method to classify depression severity. It assesses for the presence of several symptoms related to depression, such as irritability, hopelessness and decreased cognitive performance. Physical symptoms such as weight loss and fatigue are also included. This instrument has been used previously to evaluate depression severity in patients with phantom limb pain [37], as well as in other chronic pain conditions [31, 38, 39]. If the subject appears at-suicidal risk (detected by the BDI questionnaire- as defined by a score of  $\geq 1$  on question 9), the medical coverage will be contacted immediately by research staff to provide further evaluation and action to protect the subject (i.e. if the subject needs to be escorted or referred to the MGH ED Acute Psychiatry Service). In addition, if a subject has moderate to severe depression (defined by a score of  $\geq 20$  in the Beck Depression Inventory), the investigator will strongly recommend the subject search for depression management centers and encourage them to speak to their primary care physician). If the BDI questionnaire is performed over the phone (visit 16) the same procedure described above will be performed over the phone by the research staff (the research staff will discuss with the medical coverage and follow his/her plan of action according to above while subject is on the phone).

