#### *For aim 1:*

[figure not shown]
The primary outcome is PLP indexed by VAS. PLP will be analyzed using intensity of pain over time. To analyze these data, we will initially build a mixed ANOVA model in which the dependent variable will be the outcome of PLP (such as VAS) and the independent variables will be group (active tDCS-MT; sham tDCS-MT; active tDCS and covered MT; sham tDCS- covered MT), time (baseline and after treatment and follow-up) and the interaction group\*time. In addition we will add the random variable ID to account for within subject’s variability and the repeated measures on time. We will initially perform this full model and, subsequently, post-hoc comparisons with corrections for multiple comparisons will be carried out initially to test our main hypotheses. Furthermore we will test the correlation in improvement between outcomes using Pearson’s correlation tests. P-values for secondary and exploratory outcomes will be determined without corrections for multiple comparisons. Finally we will apply a path analysis [60, 61] to the primary outcome data to determine if pain reduction associated with the combined intervention (tDCS and MT) is due to direct effects versus indirect effects through improvement in secondary outcomes. We propose that a direct effect of tDCS and MT on pain can be assumed if the treatment effect cannot be explained by changes in psychological or functional outcomes. Statistical models for pain will be developed using covariates that include site center, baseline

[figure not shown]
pain, psychological changes, functional changes, and the covariate treatment (main effect of treatment). To complete the path analysis separate regression models will be run to model the effects' of treatment on each outcome alone including all the secondary outcomes. Analyses of the secondary outcomes will be conducted in an exploratory manner (no correction for multiple comparisons). For the intention-to-treat analysis, we will use a conservative method and assume that participants will not improve from the last measured point. But we will also perform a sensitive analysis for the missing data using other methods such as completers only.

*For aim 2:*

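### Carrying the last pain score forward is not assured to be conservative at the 4- and 8-week follow-up visits, because it blocks relapse as well as improvement

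*Combined protocol and SAP*

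**What the plan says.** The rule is in section VI, Statistical Analysis, For aim 1: "we will use a conservative method and assume that participants will not improve from the last measured point". It rules out improvement and gives no number to enter. A sensitivity analysis by other methods is promised, with an analysis of completers as the one example.

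The same section sets out the primary model: a mixed ANOVA of phantom limb pain VAS on group, time and their interaction, with a random subject effect. Time covers baseline, after treatment and follow-up. Post-hoc comparisons are to be corrected for multiplicity.

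The Specific Aims describe "a final 8-week follow-up period without any treatment to examine long-lasting effects of each therapy". Of Visit 16 the protocol says "This visit will be scheduled ~ four weeks (+/- 5 days) after the last MT home session", and of Visit 17 "This visit will be schedule ~eight weeks (+/- 5 days) after the last MT home session". The sample size section allows for 20% attrition.

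Pain is recorded in several ways. At treatment sessions the VAS falls under both "Before stimulation, the subject will complete the following assessments" and "After each session, subjects will complete the following assessments". It is taken again at Visits 14, 16 and 17. After Visit 14, "the co-investigator will try to contact the subjects 3 times per week to acquire pain diary and medication changes data". The diary is a separate instrument: "They will record the intensity of the strongest episode".

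**The concern.** Carry-forward is cautious while treatment is still building an effect, since someone who leaves early is given no credit for later gain. After treatment stops, the risk is the other way round: benefit may fade. A subject lost after Visit 14 keeps the end-of-treatment score, so any fading goes unrecorded in that subject. The follow-up period exists to detect exactly that fading.

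At stake is how the follow-up contrasts are read. Under some loss patterns they would show a lasting benefit that is not there; under others they would understate a real one. A reader told that the method is conservative would rule out the first case without grounds.

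**Working it through.** **Inputs from the documents (Sample size calculation).** Means 5.2 and 6.4, a difference of 1.2; SDs 1.5 and 1.6, pooled SD √((1.5² + 1.6²)/2) = 1.55; two-sided alpha 0.05; power 80%; attrition 20%.

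**The plan's own figure.** n per group = 2 × (1.96 + 0.842)² × 1.55² / 1.2² = 26.2, so 27 per group and 108 in total. Then 27 × 1.2 = 32.4, so 33 per group and 132 in total. Both stated totals reproduce.

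**Which comparison the 1.2 belongs to.** The reference study compared the combined treatment with visual illusion alone, so 1.2 is combined against a single therapy. The documents give no figure for combined against double sham.

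**Assumptions not in the documents.** Within-subject correlation 0.5. *Decay* means a benefit of 1.2 at end of treatment, 0.6 at Visit 16 and none at Visit 17. *Lasting* means 1.2 throughout. Loss is random, equal in the two arms, and written as per cent lost before end of treatment / before Visit 16 / after Visit 16. Those lost before end of treatment carry baseline.

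**Formula.** Bias of the carried contrast (active minus control, negative favours active) = pA(LA − FA) − pC(LC − FC), where p is the share lost, L the mean carried value and F the mean true value at that visit.

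| Pattern | Week-8 bias | Carried against true |
|---|---|---|
| Decay, 0/20/0 | 0.20 × (−1.2) = −0.24 | −0.24 against 0 |
| Decay, 10/5/5 | 0.05 × (−1.2) + 0.05 × (−0.6) = −0.09 | −0.09 against 0 |
| Lasting, 10/5/5 | 0.10 × (+1.2) = +0.12 | −1.08 against −1.20 |

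At Visit 16 under decay the true contrast is −0.60. The bias is 0.20 × (−0.6) = −0.12 with 0/20/0 loss, and 0.10 × (+0.6) + 0.05 × (−0.6) = +0.03 with 10/5/5. The sign can differ even between the two follow-up visits.

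**Uncorrected rejection at week 8, true difference zero, 33 per arm.** Mixing carried and true values adds a little variance in the active arm.
- 0/20/0: added variance 0.2 × 0.8 × 1.2² = 0.23; SE = √((2 × 2.405 + 0.23)/33) = 0.39; shift 0.24/0.39 = 0.61 SE; rejection about 9.4%. Simulations of 20,000 runs gave 9.0% to 9.4%.
- 10/5/5: SE 0.385; shift 0.23 SE; rejection about 5.6%. Simulations gave 5.2% to 5.8%.

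**With a multiplicity correction.** The plan does not name one, so Bonferroni over six pairs is assumed. Simulated family-wise rates at week 8 across four groups: no loss 4.0%; decay 10/5/5 4.4%; decay 0/20/0 6.0%; a 1.5-point relapse shared by all groups with unequal loss of 30/20/20/10% (combined, each single therapy, double sham) about 7%. These runs put the 1.2 on combined against double sham and gave single therapies half of it, so they are illustrative only.

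**If unobserved worsening drives the loss** (same illustrative set-up, decay, 27.5% lost in the combined group and 13.3% in double sham), the week-8 contrast, truly zero, is −0.47 with carry-forward, −0.17 with likelihood and −0.13 with completers.

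**The case against.** The case against giving this much weight has real force.

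- *The text bars only improvement, so a worse value could be entered.* True, and the relapse bias would then shrink or vanish. But the plan names no worse value, and carrying the last one is the ordinary reading.
- *Which score is last is clear enough.* Largely accepted. The outcome is phantom limb pain VAS and the model times are listed, so the last VAS at a modelled time is the sensible reading; the diary measures something else. A reader might infer that the rule cannot be run at all. The documents do not support that: one sentence of wording would settle it.
- *The 9% is for an uncorrected single contrast, while the plan corrects its post-hoc tests.* This stands. The inflation left after correction is small.
- *The larger biases need particular patterns.* This stands too. The −0.24 puts all loss after treatment, with complete fading. Visit 16 may be done by telephone, and staff attempt contact three times a week, both of which work against such loss. The spread pattern gives only −0.09.
- *A sensitivity analysis is already planned.* In part. With random loss, completers came within 0.01 of the truth in the two-arm cases. With loss driven by unseen relapse they are biased, and nothing named lets pain return.
- *Likelihood does no better than completers in that last case.* Correct (−0.17 against −0.13), though both are far closer to zero than carry-forward at −0.47. This is why the change of primary analysis is not enough alone.

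**Conclusion.** The point holds in limited form: the plan attributes to its intention-to-treat rule a property that the rule does not assure at the two follow-up visits. Under the assumptions shown, the week-8 bias lies between −0.24 and +0.12 VAS points with equal loss, against a planned difference of 1.2. The effect on error rates after correction is modest, about 4% to 7% family-wise against 4% with no loss. The end-of-treatment contrast is not affected by later relapse.

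A reader might go further and infer that the rule favours active treatment in this trial, or that it nearly doubles the false-positive rate. The documents support neither. They give no fading pattern and no loss by arm, time or reason; the same rule works against treatment if benefit lasts; and the 9% ignores the planned correction. The decay, correlation and loss splits are assumptions, and four-group figures that place 1.2 on combined against double sham are illustrative. This should be fixed because the label is unsupported and a better method is already in the plan, not because a large bias has been shown.

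**What to change.** 1. Make the primary intention-to-treat analysis the mixed model already planned (group, time, interaction, random subject), fitted by likelihood to all randomised subjects and all observed visits, including Visit 16, with no imputation. State that it is valid under missing at random.
2. Keep carry-forward as a sensitivity analysis, defining the carried value as the last phantom limb pain VAS at a modelled time. Keep completers as another.
3. Add one sensitivity analysis that lets pain return after loss, specified in advance. Multiple imputation based on the double-sham group, or with a delta fixed beforehand, would serve. It is needed because likelihood does not protect against loss driven by unobserved relapse.
4. Report loss by arm and visit, and delete the word conservative.

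The cost is SAP wording and a little more analysis work; no new data are needed. Follow-up estimates become slightly less precise. In the illustrative four-group runs with lasting benefit and 10/5/5 loss, power for the uncorrected week-8 contrast of combined against double sham was 82.0% with likelihood and 84.6% with carry-forward. For the overall group-by-time test it was 71.4% and 71.6%.

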Each of these conditions will have the same length – 20 seconds. The fMRI session will have four runs that will contain 6 blocks (6 of each condition). The order of the conditions will be randomized. For the analysis we will determine the ROI of interest (primary sensory motor cortex of the lower limbs) and first determine the ratio of activation between the MOV-LEG and MIR-LEG (in the respective ROI of interest – contralateral to the respective leg). Using this coefficient we will then compare across the different conditions. Our hypothesis is that the combined group (tDCS and mirror therapy) will have a greater activation than any therapy alone

and also the no therapy group (sham tDCS and covered mirror). This effect will also be correlated with pain reduction.

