The secondary outcomes are other pain measurements, psychological, neuropsychological and quality of life measurements and neurophysiological markers (as indexed by TMS and fMRI). Functional neuroimaging data will be analyzed using both Freesurfer image analysis suite combined with the FS-FAST functional data analysis package (Massachusetts General Hospital, Charlestown, MA) (<http://surfer.nmr.mgh.harvard.edu/>) and with Brain Voyager QX 1.9 software package (Brain Innovation, Maastricht, Netherlands). Briefly, a high resolution anatomical T1-weighted anatomical volume is used to reconstruct a cortical surface mesh and then inflated to allow viewing of sulcal activation. The functional preprocessing includes 3-D motion correction using the first volume alignment, high pass filtering to remove temporal linear trends, correction for slice time acquisition and spatial smoothing (Gaussian kernel, 5.0 mm FWHM). Subjects are screened for excessive motion (defined as a maximum tolerance of 3mm in any direction). Following co-registration of the preprocessed functional image with the high-resolution anatomical, data is transformed into standard Talairach space. Voxel time courses for each subject are fit by a general linear model (GLM) for statistical analysis. Each experimental condition is modeled by a boxcar regressor matching the condition time course. These boxcar regressors are then smoothed by a canonical hemodynamic response function [62]. Individual subject maps for each contrast of interest is generated by projecting the volume of significance values resulting from the GLM onto the reconstructed cortical surface mesh for each hemisphere in each subject. Statistical significance is set at a standard threshold criterion of  $p < 0.05$  corrected for multiple comparisons using a cluster-size threshold adjustment [63].

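### Smoothing the fMRI data before the hemispheres are separated may carry intact-leg-side signal into the affected-side leg region, by an amount that depends on a midline gap the plan does not state

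*Combined protocol and SAP*

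**What the plan says.** The image processing is described in Section VI, Statistical Analysis, for aim 2. Functional preprocessing ends with "spatial smoothing (Gaussian kernel, 5.0 mm FWHM". The next step is: "Following co-registration of the preprocessed functional image with the high-resolution anatomical, data is transformed into standard Talairach space". Then: "Voxel time courses for each subject are fit by a general linear model (GLM) for statistical analysis". The hemispheres are first treated separately after that, when individual maps are made by "projecting the volume of significance values resulting from the GLM onto the reconstructed cortical surface mesh for each hemisphere in each subject".

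Three other places set what the images must deliver.
- The fMRI entry under Description of Assessments (Section V) names the region of interest as the "primary sensory motor cortex of the lower limbs" and builds an index from the ratio of activation in the two movement conditions.
- The same entry has the participant move the non-amputated leg in both conditions, once without and once with the mirror image.
- Aim 2 in Section II looks for activation changes "between the sensory-motor cortex of the affected and unaffected side after the treatment".

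The plan mentions no hemisphere mask, smoothing along the surface, extraction from unsmoothed data or exclusion of voxels near the midline. It gives no voxel size, region boundary or distance between the two leg areas.

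**The concern.** A smoothing kernel applied to the volume takes no account of which hemisphere a voxel belongs to. The leg areas of the two hemispheres lie on facing medial walls, so a kernel whose width is similar to the gap between them averages some of each side into the other. Projecting onto separate surfaces afterwards cannot undo this.

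The task makes the mixing uneven. Only the intact leg moves, so the strong motor response is expected in the hemisphere opposite that leg, and the affected-side region lies directly across the midline from it. Signal then flows mainly from the strongly active side to the side whose reorganisation the trial wants to measure.

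Two things are at stake. A real difference between the sides, or a change in it, would be understated. And if treatment changed activation on the intact-leg side only, part of that change would also appear on the affected side, where it could be taken for reorganisation and then correlated with pain reduction, as Aim 2 plans.

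**Working it through.** The plan gives no figure for leakage across the midline, so there is nothing of its own to reproduce. The check is a simple geometric model.

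**Inputs**
- Kernel: Gaussian, 5.0 mm FWHM (Section VI, for aim 2).
- Smoothing in the volume: inferred from the order of steps, since smoothing precedes a voxel-wise model and the projection to surfaces.
- Cortical thickness t: assumed 2.5 mm, varied from 2 to 3 mm.
- Gap g between the facing sheets: assumed, varied from 1 to 6 mm.

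**Step 1, kernel SD.** s = 5.0 / (2√(2 ln 2)) = 5.0 / 2.3548 = 2.12 mm.

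**Step 2, leakage.** Treat the two leg areas as parallel sheets of thickness t, a distance g apart, with uniform signal on one of them. With Φ the normal distribution function, and averaging over depth x from 0 to t:
- own-side mean = average of Φ(x/s) − Φ((x − t)/s)
- opposite-side mean = average of Φ((x + g + t)/s) − Φ((x + g)/s)
- leakage L = opposite-side mean / own-side mean

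At t = 2.5 mm the own-side mean is 0.422.

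**Step 3, effect on a side ratio.** If the true affected-side response is half the intact-side response, the observed ratio is (1 + 0.5L) / (0.5 + L). At g = 2 mm this is (1 + 0.081) / (0.5 + 0.163) = 1.63. At g = 4 mm it is (1 + 0.011) / (0.5 + 0.022) = 1.94.

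| Assumed gap (mm) | Opposite-side mean | L at t = 2.5 mm | L for t = 3 to 2 mm | A true 2:1 reads as |
|---|---|---|---|---|
| 1 | 0.141 | 33% | 27–42% | 1.4:1 |
| 2 | 0.069 | 16% | 13–21% | 1.6:1 |
| 3 | 0.028 | 7% | 5–9% | 1.8:1 |
| 4 | 0.009 | 2% | 2–3% | 1.9:1 |
| 5 | 0.003 | 0.6% | 0.4–0.9% | 2.0:1 |
| 6 | 0.001 | 0.1% | 0.1–0.2% | 2.0:1 |

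**Step 4, asymmetry index.** With I and A the intact-side and affected-side signals, (I − A)/(I + A) is multiplied by (1 − L)/(1 + L). This is 0.72 at 2 mm, 0.96 at 4 mm and 1.00 at 6 mm.

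**Step 5, misattribution.** A change on the intact-leg side alone appears on the affected side as the fraction L of itself: 16% at 2 mm, 2% at 4 mm.

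**The case against.** The strongest objection is that the size rests on a distance the documents do not give. Over the assumed range the leakage runs from about a third of the signal to practically nothing. This stands: the point can only be stated conditionally.

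The second is that the kernel is identical in all four randomized groups and at both scans. This also stands. A reader might infer that the smoothing biases the group comparison, but nothing in the plan supports that. What remains is dilution of the side contrast and misattribution of part of a real intact-side change.

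The third is that fMRI is a secondary outcome, that secondary outcomes are analysed in an exploratory manner, and that a participant who cannot be scanned may still enrol. True, and it sets the weight of the point.

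The fourth is that the processing paragraph is explicitly a brief summary, names two software packages and never states in words that smoothing is done in the volume. The order of steps makes that the natural reading, but a fuller processing specification could settle it.

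The fifth is that the planned index is a ratio of two conditions, and the calculation above concerns a contrast between sides. Fair: the shift in that ratio, or in its change over time, has not been worked out.

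A reader might also infer that leg-region activation will be read from the projected significance values, which depend on noise as well as on effect size. The plan does not say so. It uses those values for individual subject maps, while Aim 2 and the sample size section speak of BOLD changes. What can be said is that the fMRI description does not state how activation in the region is quantified.

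**Conclusion.** The point holds as a conditional one. As written, the plan smooths before it separates the hemispheres, and nothing in it prevents mixing across the midline in the region where Aim 2 needs the sides kept apart. Under the facing-sheet model, leakage is material (about 5% or more) where the leg areas lie within about 3 mm of each other, and negligible from about 5 mm. To say that the affected-side measure is contaminated would go too far: the documents establish neither the gap nor the voxel size.

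The conclusion rests on general anatomy for the facing leg areas, on the assumed thickness and gaps, and on reading the smoothing step as volumetric. It touches a secondary, exploratory outcome only and leaves the primary VAS analysis as it is. It is a low-priority improvement, worth making because it costs so little.

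**What to change.** For the hemisphere-specific leg-region measure, do one of the following and say which in the SAP:
- extract the region mean from unsmoothed data; or
- sample the unsmoothed data onto each hemisphere's surface in FS-FAST, which the plan already names, and smooth along that surface.

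Keep volume-smoothed maps for display. Define activation in the region as percent signal change against the rest condition, so that the index has a stated unit.

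The cost is one processing setting and a sentence or two in the SAP, with no new data, visits or participants. The downside is slightly noisier vertex-level maps; averaging over the region removes most of that noise from the region measure. The change eliminates leakage caused by the kernel. It does not eliminate mixing within voxels at acquisition, so the voxel size should be stated too, and a sensitivity analysis leaving out voxels near the midline would be a useful check.
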